5 SUPPORTING DOCUMENTATION

5.1 APPENDIX 1 LIST OF ABBREVIATIONS

ADA:	anti-drug antibody
AE:	adverse event
AESI:	adverse event of special interest
AESIs:	adverse events of special interest
AFRS:	allergic fungal rhinosinusitis
ALT:	alanine aminotransferase
ANCOVA:	analysis of covariance
AST:	aspartate aminotransferase
CDG:	company drug grouping
CI:	confidence interval
CMH:	Cochran-Mantel-Haenszel
CMQ:	customized MedDRA query
CRS:	chronic rhinosinusitis
CRSwNP:	chronic rhinosinusitis with nasal polyposis
CSR:	clinical study report
CT:	computerized tomography
CV:	coefficient of variation
eCRF:	electronic case report form

HLGT:	high level group term
HLT:	high level term
HRQoL:	health-related quality of life
ICF:	informed consent form
IE:	intercurrent event
IgE:	immunoglobulin E
IMP:	investigational medicinal product
INCS:	intranasal corticosteroids
IRT:	interactive response technology
ITT:	intention-to-treat
LABA:	long-acting β 2-adrenergic receptor agonists
LAMA:	long-acting muscarinic acetylcholine receptor antagonists
LLOQ:	lower limit of quantification
LLT:	lower level term
LMK:	Lund Mackay
LS:	least square
MCID:	minimal clinically important difference
MCMC:	Markov Chain Monte Carlo
MedDRA:	medical dictionary for regulatory activities

MH:	Mantel-Haenszel
MI:	multiple imputation
NPS:	nasal polyp score
PCSA:	potentially clinically significant abnormality

PRO:	patient report outcome
PT:	preferred term
SAE:	serious adverse event
SAP:	statistical analysis plan
SCS:	systemic corticosteroids
SD:	standard deviation
SEM:	standard error of the mean
SMQ:	standardised MedDRA query
SNOT-22:	22-item sino-nasal outcome test
SOC:	system organ class
TE:	treatment-emergent
TEAE:	treatment-emergent adverse event
TSS:	total symptom score
ULN:	upper limit of normal
ULOQ:	upper limit of quantification
UPSIT:	University of Pennsylvania smell identification test
VAS:	visual analog scale
WHO-DD:	World Health Organization-drug dictionary
WOCF:	worst observation carried forward

5.2 APPENDIX 2 PARTICIPANT DISPOSITIONS

The number (%) of participants included in each of the analysis populations listed in [Table 3](#) will be summarized.

Screen failures are defined as participants who consent to participate in the study but are not subsequently randomized. The number (%) of screen failures and reasons for screen failures will be provided in the screened population.

The number (%) of participants in the following categories will be provided:

- Randomized participants
- Randomized but not exposed participants
- Randomized and exposed participants
- Participants who completed the study treatment period as per protocol

- Participants who did not complete the study treatment period as per protocol and main reason for permanent intervention discontinuation.
- Participants who completed the study period as per protocol.
- Participants who did not complete the study period as per protocol and main reason for study discontinuation.

The number (%) of exposed and not randomized participants will also be summarized.

In addition, the number (%) of participants screened, screened-failed, randomized, with permanent intervention discontinuation and with early study discontinuation will be provided by country and site.

Protocol deviations

Critical and major protocol deviations (automatic or manual) will be summarized in the randomized population.

5.3 APPENDIX 3 DEMOGRAPHICS AND BASELINE CHARACTERISTICS, PRIOR OR CONCOMITANT MEDICATIONS

Demographics, baseline characteristics, medical surgical history

The following demographics and baseline characteristics, medical and surgical history and disease characteristics at baseline will be summarized using descriptive statistics in the randomized population.

Demographic and baseline characteristics

- age in years as quantitative variable and in categories (≥ 6 - <12 , ≥ 12 - <18 , ≥ 18 - <65 , ≥ 65 years)
- gender (Male, Female)
- Race (American Indian or Alaska Native, Asian, Japanese, Black or African American, Native Hawaiian or Other Pacific Islander, White, Not reported, Unknown)
- Ethnicity (Hispanic or Latino, Not Hispanic or Latino, Not reported, Unknown)
- Region (Americas: Argentina, USA, Canada; Asia: China, Japan, India, Turkey, Saudi Arabia)
- Baseline weight (<70 , ≥ 70 - <90 , ≥ 90 kg)
- Baseline BMI (<27 , ≥ 27 kg/m²)

Baseline safety and efficacy parameters (apart from those listed above) will be presented along with the safety and efficacy summaries.

Medical (or surgical) history includes all the relevant medical (or surgical) history during the lifetime of the participant. Medical and surgical history will be coded to a LLT, PT, HLT, HLGT, and associated primary SOC using the MedDRA version currently in effect at Sanofi at the time of database lock. Allergic comorbidities will be summarized separately.

Disease characteristics at baseline

- Nasal polyp score
- Lund-Mackay score
- Nasal symptom diary scores for nasal congestion/obstruction, decreased/loss of sense of smell, rhinorrhea (anterior/posterior nasal discharge) and total symptom score (TSS) respectively
- UPSIT smell test score
- SNOT-22
- Time since first diagnosis of AFRS (years) to be derived as
(Year of randomization – Year of first diagnosis of AFRS) + (month of randomization – month of first diagnosis of AFRS)/12
- Age at onset of AFRS (years)
- Number of prior sino-nasal surgeries (0, 1, 2, ≥ 3)
- Time from last sino-nasal surgery (≤ 2 years [including surgery naive participants], >2 years) to be derived as
(Year of randomization – Year of last sino-nasal surgery) + (month of randomization – month of last sino-nasal surgery)/12
- Disease pattern (unilateral/bilateral in the endoscopy at baseline)
- Asthma comorbidity (Yes, No)

For asthma patients, provide the following:

- Age at onset of asthma (years), identified as investigator reported in the eCRF.
- Time since first diagnosis of asthma (years) to be derived as
(Year of randomization – Year of first diagnosis of asthma) + (month of randomization – month of first diagnosis of asthma)/12
- Number of courses of systemic corticosteroid (SCS) use during the past 2 years (0, 1, 2, 3, 4, ≥ 5)
A course of SCS is considered continuous if treatment is separated by less than 7 days.
- Number of days of systemic corticosteroid (SCS) use during the past 2 years (0, >0 - ≤ 7 , >7 - ≤ 14 , >14 - ≤ 21 , >21 - ≤ 28 , >28)

Prior or concomitant medications and procedures

All medications will be coded using the World Health Organization-Drug Dictionary (WHO-DD) using the version currently in effect at Sanofi at the time of database lock.

All procedures will be coded to a PT and associated primary SOC using the version of MedDRA currently in effect at Sanofi at the time of database lock.

Prior medications/procedures are those the participant received prior to first IMP intake. Prior medications/procedures can be discontinued before first administration or can be ongoing during treatment period.

Concomitant medications/procedures are any medications/procedures received by the participant concomitantly to the IMP from the first administration of IMP to the last IMP intake +98 days.

Post-treatment medications/procedures are those the participant received in the period running from the end of the concomitant medications/procedures period up to the end of the study.

A given medication/procedure can be classified as a prior medication/procedure and/or as a concomitant medication/procedure and/or as post-treatment medication/procedure. If it cannot be determined whether a given medication/procedure was taken prior or concomitantly or post, it will be considered as prior, concomitant, and post-treatment medication.

The prior and concomitant medications will be summarized for the randomized population, by anatomic and therapeutic level. Participants will be counted once in each ATC category (anatomic or therapeutic) linked to the medication.

The prior and concomitant procedures will be summarized for the randomized population, by primary SOC and PT.

Background intervention

Participants that are using background INCS must have a stable dose regimen for at least 1 month at the time of V1. From the time of screening throughout the study treatment period, they should not change their background medications.

Intranasal corticosteroids (other than nasal spray) such as drops, stents, or devices are not allowed as background treatment.

The compliance of intranasal corticosteroids spray used from 1 month before the screening visit to Week 52, which is defined as the (number of days intranasal corticosteroids spray used during the period)/(number of days within the period) \times 100%, will be summarized by intervention group for participants with stable use of intranasal corticosteroids spray at the screening visit.

Prohibited medications

The following concomitant treatments are not permitted during the screening period and the study treatment period:

- Intravenous immunoglobulin (IVIG) therapy.
- Any systemic immunosuppressive treatment, such as methotrexate, cyclosporine, mycophenolate, tacrolimus, etc.
- Initiation of allergen immunotherapy.
- Intranasal corticosteroid drops; intranasal steroid emitting devices/stents; nasal spray using Exhalation Delivery System such as Xhance.
- All forms of systemic steroids are prohibited during screening and study treatment period except that a short term (<2 weeks) oral corticosteroids are allowed only in study treatment period as rescue medication.
- Live, attenuated vaccines.
- Other monoclonal antibodies (biological immunomodulators), including but not limited to anti-IgE, anti-IL-5 and anti-TNF, etc.
- Systemic antifungals and antibiotics are prohibited during screening and study treatment period except for rescue use.

The concomitant prohibited medications will be summarized for the randomized population, by category (specified as above) and standardized medication name (sorted by decreasing frequency in the dupilumab group within each category).

Rescue medications/procedures

During the study treatment and follow-up periods, based on clinical evaluation, in case of worsening of signs and/or symptoms requiring medical intervention, the Investigator may consider rescue treatment with:

- Systemic antibiotics (up to 2 weeks) in case of acute infection.
- Short term courses (prednisone or prednisolone up to 2 weeks) of oral corticosteroids for AFRS or short courses of oral corticosteroids to treat other serious coexisting diseases (such as asthma exacerbation).
- Short term (≤ 4 weeks) systemic antifungal treatment based on participant's tolerability.
- Intranasal corticosteroids spray (initiation of INCS spray or change in dosing of a background INCS spray during the study period).
- Sino-nasal surgery for AFRS (8 weeks of IMP treatment is recommended prior to surgery to allow onset of treatment effect). For participants who undergo or are planned for surgery for AFRS, the Investigator may decide to continue IMP up to the time of surgery or end of treatment whichever date comes first. At the time of surgery, the participants will be permanently discontinued from study treatment.

The rescue medications will be summarized for the randomized population, by category (specified as above) and standardized medication name (sorted by decreasing frequency in the dupilumab group within each category).

The rescue procedures will be summarized for the randomized population, by primary SOC (sorted by internationally agreed order) and PT (sorted by decreasing frequency in the dupilumab group within each SOC).

5.4 APPENDIX 4 DATA HANDLING CONVENTIONS

Analysis windows for time points

The following analysis windows will decide how the scheduled and/or unscheduled visits will be used in the by-visit analyses of efficacy, safety, PK and ADA variables.

A measurement (scheduled or unscheduled) will be used if it is available and measurement date is within the analysis window.

After applying these time windows, if multiple assessments are associated to the same time point, the closest from the targeted study day will be used. If the difference is a tie, the value after the targeted study day will be used. If multiple valid values exist within a same day, then the first value of the day will be selected.

If there is no measurement for a given parameter in an analysis window, data will be considered missing for the corresponding visit.

Efficacy assessment

For the efficacy assessment, the reference date for the derivation of relative days of events or findings will be the day of first administration of intervention. If a participant was randomized but not treated, the reference date of efficacy assessment will be the randomization day for that participant.

For efficacy variables other than daily eDiary data (Nasal symptom diary), all available values of scheduled measurements will be assigned to the appropriate visit window according to [Table 7](#).

Table 7 - Analyses window definition for efficacy variables

Scheduled visit post baseline	Targeted study day	Analysis window in study days			
		Nasal Endoscopy, SNOT-22	CT scan	UPSIT	VAS for rhinosinusitis
Week 2 (Visit 3)	15			1+ to 49	1+ to 49
Week 12 (Visit 4)	85	1+ to 126		50 to 126	50 to 126
Week 24 (Visit 5)	169	127 to 210	1+ to 266	127 to 266	127 to 210
Week 36 (Visit 6)	252	211 to 307			211 to 307

Scheduled visit post baseline	Targeted study day	Analysis window in study days				
		Nasal Endoscopy, SNOT-22	CT scan	UPSiT	VAS for rhinosinusitis	
Week 52 (Visit 7)	364	308 to 405	>266	267 to 405	308 to 405	
Week 64 (Visit 8)	448	>405		>405	>405	

Study days are calculated considering Day 1 as the day of first administration of intervention. For participants randomized but not treated, the randomization day is considered as Day 1.

1: up to 1st dose date/time; 1+: after 1st dose date/time;

For daily eDiary data (Nasal symptom diary), the time period used to calculate the monthly average score is summarized in [Table 8](#) below.

Table 8 - Monthly average of daily nasal symptom diary variables

Analysis visit	Targeted study day	Day range for calculating monthly average score
Week 4	29	2-29
Week 8	57	30-57
Week 12	85	58-85
Week 16	113	86-113
Week 20	141	114-141
Week 24	169	142-169
Week 28	197	170-197
Week 32	225	198-225
Week 36	253	226-253
Week 40	281	254-281
Week 44	309	282-309
Week 48	337	310-337
Week 52	365	338-365
Week 56	393	366-393
Week 60	421	394-421
Week 64	449	422-449

Study days are calculated considering Day 1 as the day of first administration of intervention. For participants randomized but not treated, the randomization day is considered as Day 1.

Safety assessment

For the safety assessment, the reference date for the derivation of relative days of events or findings will be the date of first administration of intervention. Selected safety variables will be summarized by the analysis window defined in [Table 9](#) for the by visit descriptive analysis.

Table 9 - Analyses window definition for safety variables

Scheduled visit post baseline	Targeted study day	Analysis window in study days	
		Vital signs	Laboratory (hematology, biochemistry, urinalysis)
Week 12 (Visit 4)	85	1+ to 126	1+ to 126
Week 24 (Visit 5)	169	127 to 210	127 to 266
Week 36 (Visit 6)	252	211 to 307	
Week 52 (Visit 7)	364	308 to 405	267 to 405
Week 64 (Visit 8)	448	>405	>405

Study days are calculated considering Day 1 as the day of first administration of intervention.

1+: up to 1st dose date/time; 1+: after 1st dose date/time;

Pharmacokinetics/immunogenicity/biomarker assessment

For the pharmacokinetics/immunogenicity/biomarker variables summary, the reference date for the derivation of relative days of measurements will be the date of first administration of intervention. Pharmacokinetics/immunogenicity/biomarker variables will be summarized by the analysis window defined in [Table 10](#) for the by visit descriptive analyses.

Table 10 - Analyses window definition for PK/ADA/biomarker variables

Scheduled visit post baseline	Targeted study day	Analysis window in study days	
		PK, ADA	Serum total IgE and fungal specific IgE,
Week 12 (Visit 4)	85	1+ to 126	1+ to 126
Week 24 (Visit 5)	169	127 to 266	127 to 266
Week 36 (Visit 6)	252		
Week 52 (Visit 7)	364	267 to 405	>266
Week 64 (Visit 8)	448	>405	

Study days are calculated considering Day 1 as the day of first administration of intervention.

1+: up to 1st dose date/time; 1+: after 1st dose date/time;

Unscheduled visits

Unscheduled visit measurements of laboratory data and vital signs will be used for computation of baseline, the last on-treatment value, analysis according to PCSAs, and the shift summaries for safety. They will also be included in the by-visit summaries if they are re-allocated to scheduled visits.

5.5 APPENDIX 5 SAMPLE SAS CODE

Part 1: Mantel-Haenszel method

```
proc freq data=ads;
  tables strata1*strata2*treat*bin_end / commonriskdiff (test=mh cl=mh) alpha=0.05;
  ods output CommonPdiff=mhdiff CommonPdiffTests=mhdifftest;
run;
```

5.6 APPENDIX 6 SELECTION CRITERIA FOR AE/MEDICATION GROUPINGS

Table 11 - List of PTs or medications for CMQs/CDGs

Grouping	Preferred Term/Medication Code	Preferred Term/Medication
Conjunctivitis	10001257	Adenoviral conjunctivitis
Conjunctivitis	10010725	Conjunctival irritation
Conjunctivitis	10010726	Conjunctival oedema
Conjunctivitis	10010736	Conjunctival ulcer
Conjunctivitis	10010741	Conjunctivitis
Conjunctivitis	10010744	Conjunctivitis allergic
Conjunctivitis	10010745	Conjunctivitis chlamydial
Conjunctivitis	10010749	Conjunctivitis gonococcal neonatal
Conjunctivitis	10010754	Conjunctivitis tuberculous
Conjunctivitis	10010755	Conjunctivitis viral
Conjunctivitis	10018258	Giant papillary conjunctivitis
Conjunctivitis	10021629	Inclusion conjunctivitis
Conjunctivitis	10030861	Ophthalmia neonatorum
Conjunctivitis	10048908	Seasonal allergy
Conjunctivitis	10049458	Herpes simplex virus conjunctivitis neonatal
Conjunctivitis	10051625	Conjunctival hyperaemia
Conjunctivitis	10053991	Inclusion conjunctivitis neonatal
Conjunctivitis	10061784	Conjunctivitis bacterial
Conjunctivitis	10062889	Pingueculitis
Conjunctivitis	10063669	Photoelectric conjunctivitis
Conjunctivitis	10067317	Oculorespiratory syndrome
Conjunctivitis	10067817	Acute haemorrhagic conjunctivitis
Conjunctivitis	10069166	Blebitis
Conjunctivitis	10071570	Ligneous conjunctivitis
Conjunctivitis	10074701	Noninfective conjunctivitis

Grouping	Preferred Term/Medication Code	Preferred Term/Medication
Conjunctivitis	10075264	Oculoglandular syndrome
Conjunctivitis	10080825	Conjunctivitis fungal
Conjunctivitis	10084034	Conjunctival suffusion
Conjunctivitis	10084038	Giant fornix syndrome

Abbreviations: CAS : Chemical Abstract Service Registry Number RECNO : Drug Record Number

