8.3.6 Adverse event of special interest

Adverse event of special interest

An AESI is an AE (serious or nonserious) of scientific and medical concern specific to the Sponsor's product or program, for which ongoing monitoring and immediate notification by the Investigator to the Sponsor is required. Such events may require further investigation in order to characterize and understand them. Adverse events of special interest may be added, modified, or removed during a study by protocol amendment. For these AESIs, the Sponsor will be informed immediately (ie, within 24 hours), per SAE notification described in [Section 10.3](#), even if not fulfilling a seriousness criterion, using the corresponding screens in the eCRF.

AESIs for this study include:

- Anaphylactic reactions.
- Systemic hypersensitivity reactions.
- Helminthic infections.
- Any severe type of conjunctivitis or blepharitis.

- Keratitis.
- Clinically symptomatic eosinophilia (or eosinophilia associated with clinical symptoms).
- Pregnancy of a female participant entered in a study as well as pregnancy occurring in a female partner of a male participant entered in a study with IMP
 - Pregnancy occurring in a female participant entered in the clinical trial or in a female partner of a male participant entered in the clinical trial. It will be qualified as an SAE only if it fulfills one of the seriousness criteria.
 - In the event of pregnancy in a female participant, IMP should be discontinued.
 - Follow-up of the pregnancy in a female participant or in a female partner of a male participant is mandatory until the outcome has been determined.
 - Abnormal pregnancy outcomes (eg, spontaneous abortion, fetal death, stillbirth, congenital anomalies, ectopic pregnancy) are considered SAEs.
- Significant ALT elevation
 - ALT $>5 \times$ ULN in participants with baseline ALT $\leq 2 \times$ ULN;
OR
 - ALT $>8 \times$ ULN if baseline ALT $>2 \times$ ULN.
- Symptomatic overdose (serious or nonserious) with IMP
 - An overdose (accidental or intentional) with the IMP is an event suspected by the Investigator or spontaneously notified by the participant and defined as at least twice the maximum prescribed daily dose, within the intended therapeutic interval. “The circumstances (ie, accidental or intentional) should be clearly specified in the overdose form”.

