Anaphylactic reaction	Anaphylactic reaction algorithmic approach (Introductory Guide for Standardized MedDRA Queries (SMQs) Version 18.1): includes anaphylactic reaction narrow SMQ (20000021) terms and programmatic identification of cases based on occurrence of at least two preferred terms meeting the algorithm criteria occurring within 24 hours of each other. The latter cases identified using the algorithm will undergo blinded medical review taking into account the timing of events relative to each other and to IMP administration for final determination of an anaphylactic reaction or not.
Systemic hypersensitivity reactions	SMQ [20000214] hypersensitivity narrow search and [AE corrective treatment/therapy = 'Y' or Action taken with IMP = 'Drug withdrawn' or Action taken with IMP = 'Drug interrupted'] followed by blinded medical review (documented process) for selection of relevant systemic hypersensitivity events
Helminthic infections	CMQ10544 based on HLGT as "Helminthic disorder"
Any severe type of conjunctivitis	CMQ10498 based on PTs (See Appendix 6) ^a and "Severe" ticked in Adverse Events eCRF page
Any severe type of blepharitis	CMQ10497 based on HL as "Lid, lash and lacrimal infections, irritations and inflammations" and "Severe" ticked in Adverse Events eCRF page
Keratitis	CMQ10642 based on the following PTs [keratitis, allergic keratitis, ulcerative keratitis, atopic keratoconjunctivitis, herpes ophthalmic, ophthalmic herpes simplex, corneal infection] ^a
Clinically symptomatic eosinophilia (or eosinophilia associated with clinical symptoms) ^b	CMQ10641 based on HL = Eosinophilic disorders or PT = Eosinophil count increased followed by blinded medical review
Pregnancy of female participants entered in a study as well as pregnancy occurring in a female partner of a male participant entered in a study with IMP	"Pregnancy" or "Partner Pregnancy" checked on the Pregnancy eCRF page as reported by the investigator

AESIs and other AEs of interest	Selection
Significant ALT elevation	"ALT increase" and AESI answer "Yes" checked on AE eCRF as reported by the Investigator (ALT >5 × ULN in participants with baseline ALT ≤2 × ULN; OR ALT >8 × ULN if baseline ALT >2 × ULN)
Symptomatic overdose with IMP	Symptomatic Overdose is answered Yes, with Overdose of Study Treatment answered Yes on AE eCRF.
Other selected AE Grouping	

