Serious injection site reactions or severe injection site reactions that last longer than 24 hours	HLT = 'Injection site reactions' and either with serious status, or with severe status and (AE end date/time - AE start date/time) ≥24 hours or ongoing
Severe or serious infection	Primary SOC = 'Infections and infestations' and with severe or serious status
Parasitic infection	Infection type "Parasitic" checked on eCRF "Infection Event Form"
Opportunistic infection	Has the AE been assessed as opportunistic infection? is answered Yes on eCRF "Infection Event Form"
Drug-related hepatic disorder	SMQ [20000006] Drug-related hepatic disorders- narrow
Injection site reactions	HLT = 'Injection site reactions'
Malignancy	SMQ [20000091]- Malignant or unspecified tumors narrow
Conjunctivitis (narrow)	CMQ10644 based on the following PTs [Conjunctivitis, Conjunctivitis allergic, Conjunctivitis bacterial, Conjunctivitis viral, Atopic keratoconjunctivitis] ^a
Conjunctivitis (broad)	CMQ10645 based on the following PTs [Conjunctivitis, Conjunctivitis allergic, Conjunctivitis bacterial, Conjunctivitis viral, Atopic keratoconjunctivitis, Blepharitis, Dry eye, Eye irritation, Eye pruritus, Lacrimation increased, Eye discharge, Foreign body sensation in eyes, Photophobia, Xerophthalmia, Ocular hyperaemia, Conjunctival hyperaemia] ^a
Conjunctivitis (FDA) ^c	CMQ10643 based on the following PTs [Conjunctivitis, Conjunctivitis allergic, Conjunctivitis bacterial, Conjunctivitis viral, Eye irritation, Eye inflammation, Giant papillary conjunctivitis] ^a
Keratitis (FDA) ^c	CMQ30102 based on the following PTs [keratitis, allergic keratitis, ulcerative keratitis, atopic keratoconjunctivitis, ophthalmic herpes simplex] ^a

a The list of terms may be adjusted according to MedDRA version changes

b All cases of Eosinophilia will be included in the analysis, where cases associated with clinical symptoms will be further described in the CSR

c Labeling subgroup of preferred terms included in the USPI for Dupixent.

The following summaries will be provided:

- All TEAEs, by selected standardized MedDRA query (SMQ)/Customized MedDRA query (CMQ) and PT, showing the number (%) of participants with at least 1 PT.
- For each AESI and other selected AE groupings,
 - Number (%) of participants with any TEAE
 - Number (%) of participants with any serious AE (regardless of treatment-emergent status)

- Number (%) of participants with any treatment-emergent serious AE

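### The term list for the severe conjunctivitis AESI includes Seasonal allergy, so a severe non-eye event would be tabulated as severe conjunctivitis

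*SAP*

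**What the plan says.** Protocol Section 8.3.6 lists "Any severe type of conjunctivitis or blepharitis" among the adverse events of special interest. Protocol Section 2.3.2 names conjunctivitis among the identified adverse reactions to dupilumab.

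SAP Section 3.6.2, Table 6, gives the rule for the conjunctivitis part. The term list is "CMQ10498 based on PTs (See Appendix 6"), and the event must also have Severe "ticked in Adverse Events eCRF page". The row states no further step.

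The terms are in SAP Appendix 6 (Section 5.6), under the title "Table 11 - List of PTs or medications for CMQs/CDGs". All are filed under the grouping Conjunctivitis. One of them is "Seasonal allergy", code 10048908. The SAP gives no reason for including it.

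Table 6 also defines separate conjunctivitis groupings (narrow, broad and FDA) and two keratitis groupings. The narrow one, for example, is "CMQ10644 based on the following PTs [Conjunctivitis, Conjunctivitis allergic, Conjunctivitis bacterial, Conjunctivitis viral, Atopic keratoconjunctivitis".

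**The concern.** Seasonal allergy is a general allergic condition. It may involve the eyes, but the term does not say so, and hay-fever symptoms confined to the nose could be coded to it. Under the rule as written, the only filter after the term match is the severity tick, and a severity tick says nothing about which organ was affected.

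The same table sends three other AESIs to blinded medical review: anaphylactic reaction (for cases found by the algorithm), systemic hypersensitivity, and eosinophilia. No such step is stated here, so nothing in the rule would take out a severe seasonal allergy event without eye findings.

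What is at stake is the accuracy of one safety category. Conjunctivitis is a known reaction to this drug, so readers will look at this row, and in a small trial a single event shows.

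**Working it through.** No figure in the plan needs to be reproduced. The check compares term lists and then follows the rule through.

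**1. Comparing the lists.** Inputs: Table 11 (SAP Appendix 6) and the five conjunctivitis and keratitis lists spelled out in SAP Table 6.

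| List | Terms | Of these, in Table 11 | Contains Seasonal allergy | Contains Atopic keratoconjunctivitis |
|---|---|---|---|---|
| Table 11 (CMQ10498) | 29 | n/a | Yes | No |
| Conjunctivitis, narrow (CMQ10644) | 5 | 4 | No | Yes |
| Conjunctivitis, broad (CMQ10645) | 16 | 5 | No | Yes |
| Conjunctivitis, FDA (CMQ10643) | 7 | 5 | No | No |
| Keratitis AESI (CMQ10642) | 7 | 0 | No | Yes |
| Keratitis, FDA (CMQ30102) | 5 | 0 | No | Yes |

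Seasonal allergy appears in Table 11 and in none of the other five. Seven Table 11 terms do not have conjunctiva or conjunctivitis in their name. Six of these are ocular terms (ophthalmia neonatorum, pingueculitis, oculorespiratory syndrome, blebitis, oculoglandular syndrome, giant fornix syndrome). Seasonal allergy is the seventh.

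**2. Following one event through the rule.** SAP Section 3.6.2 counts an event as treatment-emergent if it develops, worsens or becomes serious in the treatment-emergent period. Suppose a participant's seasonal allergy worsens in that period and the investigator marks it Severe.

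- Term match against Table 11: yes.
- Severe on the adverse event page: yes.
- Medical review: none stated.
- Result: counted as severe conjunctivitis, but in none of the narrow, broad or FDA conjunctivitis groupings.

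**3. Does a footnote cover it?** Footnote a to Table 6 allows the lists to be adjusted for MedDRA version changes. It neither explains why the term is there nor provides for removing it on content grounds.

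**4. Could the text extraction be the cause?** Table 11 breaks across a page, but its codes ascend throughout and no row looks lost or blacked out. Missing rows could not in any case explain a term that is present.

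**5. Size.** Protocol Section 4.1 plans 31 per arm. If all are treated, one participant counted this way changes that arm's rate by 1/31 = 3.2 percentage points. This is the weight of a single participant. It does not say how likely the event is, and the documents give no rate from which to estimate that.

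**The case against.** **Limits that stand.** Several things keep the effect small.

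- The event must be treatment-emergent and graded severe, which Protocol Appendix 3 reserves for events that stop normal daily activity. Stable pre-existing seasonal allergy would not count.
- SAP Section 3.6 makes the safety analysis descriptive with no testing, so no formal inference changes.
- SAP Section 3.6.2 shows AESIs by preferred term where applicable, and all TEAEs by query and preferred term. A careful reader would see the term.
- Investigator-reported AESIs are summarized separately and do not depend on Table 11.
- The lack of stated review is not peculiar to this row. Severe blepharitis, keratitis and helminthic infection have none either.
- CMQ10498 is a company query, and the reason for including this term may lie in a query definition that the documents do not show.

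These points limit the consequence. They do not make the category count right, because the row total would still include the event.

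**Stronger readings that the documents do not support.**

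*That severe atopic keratoconjunctivitis goes unreported.* A reader might infer this from its absence from Table 11. But it is in the Keratitis AESI list, which has no severity filter, so it is an AESI at any grade. It is also in the narrow and broad conjunctivitis groupings, and SAP Section 3.6.2 reports every AESI and selected grouping by maximum intensity. The event is outside one row but is not lost.

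*That the error is frequent or favours one arm.* A reader might infer that seasonal allergy is common in these participants, or more likely to flare where disease is less controlled. The documents require fungal sensitization and record allergic comorbidities, but they give no frequency of seasonal allergy and no link to disease control. No direction of bias can be claimed.

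*That the broad list with a Severe filter should replace Table 11.* It would keep 5 of the 29 terms and lose 29 − 5 = 24, including adenoviral, chlamydial, fungal and giant papillary conjunctivitis. It would add 16 − 5 = 11 terms, among them Dry eye, Photophobia and Blepharitis, and severe blepharitis already has its own AESI row. That would misclassify more than it corrects.

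**Conclusion.** The point holds as a minor defect in the definition of one AESI. Seasonal allergy does not belong, on its face, in a list that selects severe conjunctivitis, and with no review stated the rule would count it. The conclusion rests on Table 11 being applied as printed and on no unwritten review step for this row. The size is 3.2 percentage points in an arm of 31 for each such participant. The number of such participants is unknown and may be zero. Efficacy results and hypothesis tests are unaffected, and so is site reporting of AESIs, which follows the protocol definition and not this list. The absence of atopic keratoconjunctivitis from the list is a matter for clarification only.

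**What to change.** Before database lock, remove Seasonal allergy from the list used to select the severe conjunctivitis AESI, leaving 28 terms, and record the change and its reason in the SAP. If pooling with other trials needs the company query, keep the unmodified CMQ10498 as a secondary display. The two counts can differ only for a participant whose sole qualifying event is a severe seasonal allergy.

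Optionally, add a note to Table 6 or Table 11 that atopic keratoconjunctivitis is counted under the Keratitis AESI and in the narrow and broad conjunctivitis groupings.

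The cost is one deleted term, a sentence of explanation and possibly one extra table. The downside is a small departure from the company-wide query. Making the change before unblinding avoids having to reclassify an AESI with treatment assignments known.
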